7.3. Method of Treatment Assignment

Subjects will be randomized to either active or placebo at the start of each cohort in accordance with the randomization schedule generated by Clinical Statistics, prior to the start of the study, using validated internal software.

A description of each regimen in Part A, Part B and Part C is provided respectively in [Table 11](#), [Table 12](#), [Table 13](#), [Table 14](#) below.

Table 11 Part A Single Ascending Dose (IV Bolus) in Males:*Cohort 1-8*

Subject	Period 1 (sentinels)	Period 1 (remainder)						
X	Placebo							
X	Dose 1							
X		Dose 1						
X		Dose 1						
X		Dose 1						
X		Dose 1						
X		Dose 1						
X		Placebo						

Table 12 Part B Multiple Ascending Dose (i.v. bolus followed by an i.v. infusion) in Males:

Cohort	No. of Subjects	Day 1	Day 2	Day 3	Day 4	Day 5	Day 6	Day 7
Cohort 9 (sentinel)	1	Dose 1	Dose 1	Dose 1	Dose 1	Dose 1	Dose 1	Dose 1
	1	Placebo						
Cohort 9 (remaining)	5	Dose 1						
	1	Placebo						
Cohort 10 (sentinel)	1	Dose 2						
	1	Placebo						
Cohort 10 (remaining)	1	Dose 2						
	1	Placebo						
Cohort 11 (sentinel)	5	Dose 2						
	1	Placebo						
Cohort 11 (remaining)	1	Dose 3						
	1	Placebo						
Cohort 12 (sentinel)	5	Dose 3						
	1	Placebo						
Cohort 12 (remaining)	1	Dose 4						
	1	Placebo						
	5	Dose 4						
	1	Placebo						

Part C: Single (i.v. bolus) or Multiple Dose (i.v. bolus followed by an i.v. infusion) in WONCBP:

Table 13 Cohort 13: Single (i.v. bolus) Dose

Subject	Period 1 (remainder)
X	Placebo
X	Dose 1
X	Placebo

Table 14 Cohort 14: Multiple Dose (i.v. bolus followed by an i.v. infusion)

Cohort	No. of Subjects	Day 1	Day 2	Day 3	Day 4	Day 5	Day 6	Day 7
Cohort 14	6 2	Dose 1 Placebo						

7.4. Blinding

This will be a double-blind (Sponsor unblinded) study in which the subjects and site staff (Pharmacist unblinded to prepare study drug) will be blinded for the duration of the study, and the following will apply.

- The investigator or treating physician may unblind a subject's treatment assignment **only in the case of an emergency** OR in the event of a serious medical condition when knowledge of the study treatment is essential for the appropriate clinical management or welfare of the subject as judged by the investigator.
- Investigators have direct access to the subject's individual study treatment.
- It is preferred (but not required) that the investigator first contacts the Medical Monitor or appropriate GSK study personnel to discuss options **before** unblinding the subject's treatment assignment.
- If GSK personnel are not contacted before the unblinding, the investigator must notify GSK as soon as possible after unblinding, but without revealing the treatment assignment of the unblinded subject, unless that information is important for the safety of subjects currently in the study.
- The date and reason for the unblinding must be fully documented in the case report form (CRF)

A subject may continue in the study if that subject's treatment assignment is unblinded.

GSK's Global Clinical Safety and Pharmacovigilance (GCSP) staff may unblind the treatment assignment for any participant with an SAE. If the SAE requires that an expedited regulatory report be sent to one or more regulatory agencies, a copy of the report, identifying the participant's treatment assignment, may be sent to investigators in accordance with local regulations and/or GSK policy.

7.5. Preparation/Handling/Storage/Accountability

A description of the methods and materials required for the preparation of GSK3335065 solution for injection will be detailed in a Study Specific Technical Agreement/Memo (SSTA) or Pharmacy Manual which will be accompanied by a Quality Agreement.

No special preparation of study treatment is required.

- Only subjects enrolled in the study may receive study treatment and only authorized site staff may supply or administer study treatment. All study treatments must be stored in a secure environmentally controlled and monitored (manual or automated) area in accordance with the labelled storage conditions with access limited to the investigator and authorized site staff.
- The investigator, institution, or the head of the medical institution (where applicable) is responsible for study treatment accountability, reconciliation, and record maintenance (i.e. receipt, reconciliation and final disposition records).
- Further guidance and information for final disposition of unused study treatment are provided in the SRM.
- Under normal conditions of handling and administration, study treatment is not expected to pose significant safety risks to site staff. Take adequate precautions to avoid direct eye or skin contact and the generation of aerosols or mists. In the case of unintentional occupational exposure notify the monitor, Medical Monitor and/or GSK study contact.
- A Material Safety Data Sheet (MSDS)/equivalent document describing occupational hazards and recommended handling precautions either will be provided to the investigator, where this is required by local laws, or is available upon request from GSK.

Precaution will be taken to avoid direct contact with the study treatment. A Material Safety Data Sheet (MSDS) describing occupational hazards and recommended handling precautions will be provided to the investigator. In the case of unintentional occupational exposure notify the monitor, Medical Monitor and/or GSK study contact.

7.6. Treatment Compliance

- When the individual dose for a participant is prepared from a bulk supply, the preparation of the dose will be confirmed by a second member of the study site staff.
- When participants are dosed at the site, they will receive study treatment directly from the investigator or designee, under medical supervision. The date and time of each dose administered in the clinic will be recorded in the source documents. The

dose of study treatment and study participant identification will be confirmed at the time of dosing by a member of the study site staff other than the person administering the study treatment.

- GSK3335065 will be intravenously administered to subjects at the site. Administration will be documented in the source documents and reported in the CRF. The date and time of each bolus dose administered in the clinic, and the start / stop date and time of each infusion will be recorded in the source documents. The dose of study treatment and study subject identification will be confirmed at the time of dosing by a member of the study site staff other than the person administering the study treatment.

7.7. Concomitant Therapy

Any medication or vaccine (including over-the-counter or prescription medicines, vitamins, and/or herbal supplements) that the participant is receiving at the time of enrolment or receives during the study must be recorded along with:

- reason for use
- dates of administration including start and end dates
- dosage information including dose and frequency

The Medical Monitor should be contacted if there are any questions regarding concomitant or prior therapy.

Ibuprofen, at doses of ≤ 800 mg/day, is permitted for use any time during the study. Other concomitant medication may be considered on a case-by-case basis by the Medical Monitor.

7.8. Prohibited Medications and Non-Drug Therapies

Subjects must abstain from taking prescription or non-prescription drugs (including vitamins and dietary or herbal supplements), within 7 days (or 14 days if the drug is a potential enzyme inducer) or 5 half-lives (whichever is longer) prior to the first dose of study medication until completion of the follow-up visit, unless in the opinion of the Investigator and sponsor the medication will not interfere with the study.

The use of paracetamol is not allowed in his study.

7.9. Treatment after the End of the Study

Subjects will not receive any additional treatment from GSK after completion of the study because only healthy volunteers are eligible for study participation.

8. DISCONTINUATION CRITERIA

8.1. Discontinuation of Study Treatment

Discontinuation from treatment is “permanent”. Once a subject is discontinued, she/he shall not be allowed to restart treatment.

8.1.1. Liver Chemistry Stopping Criteria

Liver chemistry stopping and increased monitoring criteria have been designed to assure participant safety and evaluate liver event etiology. These protocol guidelines are in alignment with FDA premarketing clinical liver safety guidance:
<http://www.fda.gov/downloads/Drugs/GuidanceComplianceRegulatoryInformation/Guidances/UCM174090.pdf>.

Discontinuation of study treatment for abnormal liver tests should be considered by the investigator when a participant meets one of the conditions outlined in the algorithm or if the investigator believes that it is in the best interest of the participant.

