Liver changes	
In rats, there was centrilobular hepatocyte hypertrophy and increased liver weight at ≥ 140 mg/kg/day; and additional liver pathology changes and increases in aspartate aminotransferase, alanine aminotransferase activity and total bilirubin concentrations at ≥ 300 mg/kg/day.
 
GSK3335065 is a carboxylic acid and has the potential to form reactive acyl glucuronide metabolites which could contribute to idiosyncratic liver toxicity. An in vitro assay in human liver microsomes showed there was no turnover of GSK3335065 in microsomes and no acyl glucuronides were detected. However, an
	
Subjects with ALT or bilirubin $>1.5 \times$ULN prior to dosing will be excluded (isolated bilirubin $>1.5 \times$ULN is acceptable if bilirubin is fractionated and direct bilirubin $<35\%$). (Exclusion Criterion #1).
 
Subjects with current or chronic history of liver disease, or known hepatic or biliary abnormalities (with the exception of Gilbert's syndrome or asymptomatic gallstones) will be excluded (Exclusion Criterion #2).
 
Monitoring for ALT, AST, alkaline phosphatase and bilirubin at each dose level (Section 2 Time

Potential Risk of Clinical Significance	Summary of Data/Rationale for Risk	Mitigation Strategy
	
acyl glucuronide with a measured half-life of 2 hrs was detected in rat plasma following 7 days continuous infusion. Therefore there is a risk that this metabolite may be formed in humans. This might be of clinical concern if the total daily dose exceeds 100 mg.
	
and Events Table)
 
Stopping criteria based on LFT increases (Section 8).
 
The NOAEL for these effects is 75-fold the highest exposures proposed in this study.
 
The highest dose proposed in this study is 73.4 mg total dose on day 1 followed by 50.4 mg total dose/day (Above signals are considered an increased concern if daily dose is ≥ 100 mg).
 
Selected plasma PK samples generated during Part A will be subjected to additional analysis in order to determine if any acyl glucuronides are present. In addition, plasma, urine and bile samples will be used to generate full metabolic profiles in samples taken during the study.

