8.1.2. QTc Stopping Criteria

- The *same* QT correction formula *must* be used for *each individual participant* to determine eligibility for and discontinuation from the study. This formula may not be changed or substituted once the participant has been enrolled.
 - For example, if a participant is eligible for the protocol based on QTcB, then QTcB must be used for discontinuation of this individual participant as well.
 - Once the QT correction formula has been chosen for a participant’s eligibility, the *same formula* must continue to be used for that participant *for all QTc data being collected for data analysis*. Safety ECGs and other non-protocol specified ECGs are an exception.
- The QTc should be based on single or averaged QTc values of triplicate electrocardiograms obtained over a brief (e.g., 5-10 minute) recording period.

See the SoA for data to be collected at the time of treatment discontinuation and follow-up and for any further evaluations that need to be completed.

In addition a healthy volunteer that meets either bulleted criterion below will be withdrawn from the study:

- QTc >500 msec,
- Change from baseline: QTcF >60 msec

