8.1.3. Rechallenge

8.1.3.1. Study Treatment Restart or Rechallenge

Study treatment restart or rechallenge after liver chemistry stopping criteria are met by any participant in this study is not allowed.

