8.1.4. Additional Stopping Criteria

This section provides vital sign (blood pressure, heart rate), respiratory, oral temperature, and neuropsychiatric criteria for discontinuation of GSK 3335065 infusion. If criteria specified for action here are met, actions must be followed. Study investigators may also decide to discontinue dosing based on their clinical judgement for observations that are not specifically meet these thresholds, if they feel this is appropriate for best ensuring the safety of study subjects.

Blood Pressure:

- Resting semi-recumbent systolic blood pressure (SBP) of ≤ 80 mmHg that is confirmed (median of 3 measurements, and at least 20% decrease from baseline) and sustained for ≥ 20 min with or without symptoms of hypotension. Sustained is defined as persistent (threshold is met or exceeded on all rechecks over a 20 min period; minimum of 3 consecutive measurements over a 20 min interval)
- Resting semi-recumbent SBP ≥ 80 mmHg but ≤ 100 mHg that is confirmed (median of 3 measurements) and sustained if associated with symptoms of hypotension (e.g. fainting, lightheadedness, dizziness, anxiety)
- Hypotension requiring intervention such as Trendelenburg position w/wo fluid resuscitation
- Resting semi-recumbent SBP ≥ 180 mmHg that is confirmed (median of 3 measurements, and at least 20% increase from baseline with or without symptoms of hypertension (e.g. headaches, lightheadedness, anxiety)

Heart Rate:

- Tachycardia (resting semi-recumbent heart rate >100 bpm) of any duration associated with symptoms that the study investigator considers potentially associated with cardiac ischemia and/or hemodynamic compromise. Concerning symptoms might include chest pain, shortness of breath or lightheadedness.
- Resting semi-recumbent heart rate of ≥ 130 bpm that is confirmed (median of 3 measurements) and sustained. Sustained is defined as persistent (threshold is met or exceeded on all rechecks over a 20 min period; minimum of 3 consecutive measurements over a 10 min interval).
- Increase in resting semin-recumbent heart rate ≥ 60 bpm from the predose baseline (median of 3 measurements and sustained).

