12.2. Appendix 2: Clinical Laboratory Tests

- The tests detailed in [Table 15](#) will be performed by the Doctors Laboratory
- Additional tests may be performed at any time during the study as determined necessary by the investigator or required by local regulations.

Table 15 Protocol-Required Safety Laboratory Assessments

Laboratory Assessments	Parameters			
Hematology	Platelet Count	RBC Indices: MCV MCH	WBC count with Differential: Neutrophils Lymphocytes Monocytes Eosinophils Basophils	
	RBC Count			
	Hemoglobin			
	Hematocrit			
	Reticulocytes			
Clinical Chemistry ¹	BUN	Potassium	Aspartate Aminotransferase (AST)/ Serum Glutamic-Oxaloacetic Transaminase (SGOT)	Total and direct bilirubin
	Creatinine	Sodium	Alanine Aminotransferase (ALT)/ Serum Glutamic-Pyruvic Transaminase (SGPT)	Total Protein
	Glucose fasting ²	Calcium	Alkaline phosphatase	Albumin
	cTnI	BNP		
Routine Urinalysis	
 • Specific gravity • pH, glucose, protein, blood, ketones by dipstick • Microscopic examination (if blood or protein is abnormal) 			
Other Screening Tests	
 • HIV • Hepatitis B (HBsAg) • Hepatitis C (Hep C antibody) • FSH and estradiol (as needed in women of non-child bearing potential only)³ • Alcohol and drug screen (to include at minimum: amphetamines, barbiturates, cocaine, opiates, cannabinoids and benzodiazepines) 			
	The results of each test must be entered into the CRF.			

NOTES :

1. Details of liver chemistry stopping criteria and required actions and follow-up assessments after liver stopping or monitoring event are given in Section [8.1](#) and [Appendix 7](#) and Study Treatment Rechallenge Guidelines. All events of $ALT \geq 3 \times$ upper limit of normal (ULN) and bilirubin $\geq 2 \times$ ULN ($>35\%$ direct bilirubin) or $ALT \geq 3 \times$ ULN and international normalized ratio (INR) >1.5 , if INR measured, which may indicate severe liver injury (possible Hy's Law), must be reported as an SAE (excluding studies of hepatic impairment or cirrhosis).
2. Glucose fasting at screening and admission.
3. Local urine testing will be standard for the protocol unless serum testing is required by local regulation or IRB/IEC.

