12.7. Appendix 7: Liver Safety: Required Actions and Follow-up Assessments

Phase I Liver chemistry stopping criteria have been designed to assure subject safety and to evaluate liver event etiology (in alignment with the FDA premarketing clinical liver safety guidance).

<http://www.fda.gov/downloads/Drugs/GuidanceComplianceRegulatoryInformation/Guidances/UCM174090.pdf>.

Phase I liver chemistry stopping criteria and required follow up assessments

Liver Chemistry Stopping Criteria – Liver Stopping Event	
ALT-absolute ALT \geq 3xULN If ALT \geq 3xULN AND bilirubin ^{1,2} \geq 2xULN (>35% direct bilirubin) or INR $>$ 1.5, Report as an SAE. See additional Actions and Follow Up Assessments listed below	
Required Actions and Follow up Assessments following Liver Stopping Event	
Actions	Follow Up Assessments

 • Immediately discontinue study treatment • Report the event to GSK within 24 hours • Complete the liver event CRF, and complete an SAE data collection tool if the event also meets the criteria for an SAE² • Perform liver event follow up assessments • Monitor the subject until liver chemistries resolve, stabilise, or return to within baseline (see MONITORING below) 
MONITORING:
 
If ALT\geq3xULN AND bilirubin \geq 2xULN or INR $>$1.5
 
 • Repeat liver chemistries (include ALT, AST, alkaline phosphatase, bilirubin) and perform liver event follow up assessments within 24 hrs • Monitor subjects twice weekly until liver chemistries resolve, stabilise or return to within baseline • A specialist or hepatology consultation is 	
 • Viral hepatitis serology³ • Blood sample for pharmacokinetic (PK) analysis, obtained according to PK sampling schedule • Serum creatine phosphokinase (CPK) and lactate dehydrogenase (LDH). • Fractionate bilirubin, if total bilirubin\geq2xULN • Obtain complete blood count with differential to assess eosinophilia • Record the appearance or worsening of clinical symptoms of liver injury, or hypersensitivity, on the AE report form • Record use of concomitant medications on the concomitant medications report form including acetaminophen, herbal remedies, other over the counter medications. • Record alcohol use on the liver event alcohol intake case report form 
If ALT\geq3xULN AND bilirubin \geq 2xULN or

Liver Chemistry Stopping Criteria – Liver Stopping Event	

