
recommended
 
If $ALT \geq 3 \times ULN$ AND bilirubin $< 2 \times ULN$ and $INR \leq 1.5$:
 
 • Repeat liver chemistries (include ALT, AST, alkaline phosphatase, bilirubin) and perform liver event follow up assessments within 24-72 hrs • Monitor subjects weekly until liver chemistries resolve, stabilize or return to within baseline 	
INR > 1.5:
 
 • Anti-nuclear antibody, anti-smooth muscle antibody, Type 1 anti-liver kidney microsomal antibodies, and quantitative total immunoglobulin G (IgG or gamma globulins). • Serum acetaminophen adduct HPLC assay (quantifies potential acetaminophen contribution to liver injury in subjects with definite or likely acetaminophen use in the preceding week [James, 2009]). • Liver imaging (ultrasound, magnetic resonance, or computerised tomography) and /or liver biopsy to evaluate liver disease; complete Liver Imaging and/or Liver Biopsy CRF forms.

1. Serum bilirubin fractionation should be performed if testing is available. If serum bilirubin fractionation is not immediately available, discontinue study treatment for that subject if $ALT \geq 3 \times ULN$ and bilirubin $\geq 2 \times ULN$. Additionally, if serum bilirubin fractionation testing is unavailable, **record presence of detectable urinary bilirubin on dipstick**, indicating direct bilirubin elevations and suggesting liver injury.
2. All events of $ALT \geq 3 \times ULN$ and bilirubin $\geq 2 \times ULN$ ($> 35\%$ direct bilirubin) or $ALT \geq 3 \times ULN$ and $INR > 1.5$, if INR measured, which may indicate severe liver injury (possible 'Hy's Law'), **must be reported as an SAE (excluding studies of hepatic impairment or cirrhosis)**; INR measurement is not required and the threshold value stated will not apply to subjects receiving anticoagulants
3. Hepatitis A IgM antibody; Hepatitis B surface antigen and Hepatitis B Core Antibody (IgM); Hepatitis C RNA; Cytomegalovirus IgM antibody; Epstein-Barr viral capsid antigen IgM antibody (or if unavailable, obtain heterophile antibody or monospot testing); Hepatitis E IgM antibody

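### Section 8.1.1 leaves stopping for abnormal liver tests to the investigator, Appendix 7 requires it immediately at ALT ≥3×ULN, and the protocol does not say which governs

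*Protocol*

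**What the plan says.** Protocol Section 8.1.1, headed as the liver chemistry stopping criteria, states: "Discontinuation of study treatment for abnormal liver tests should be considered by the investigator when a participant meets one of the conditions" in an algorithm, or when the investigator judges it to be in the participant's best interest. Both triggers share the one verb. The section does not cite Appendix 7.

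Appendix 7 defines an absolute ALT of at least 3×ULN as the liver stopping event. In the column headed as required actions, the first item is "Immediately discontinue study treatment".

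Two other places send the reader to these texts. Appendix 2, note 1, names two sources, Section 8.1 and Appendix 7, in a sentence that begins "Details of liver chemistry stopping criteria and required actions and follow-up assessments after liver stopping or monitoring event are given in Section". The liver row of the risk table in Section 3.3.1 names LFT-based stopping criteria as a mitigation and points to Section 8.

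**The concern.** The two texts give different instructions for the same event. One asks the investigator to think about stopping; the other orders an immediate stop. An investigator who sees ALT at 3.5×ULN during an infusion, considers stopping and decides to continue has done what 8.1.1 asks and has breached Appendix 7.

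Liver change is an identified risk. Section 3.3.1 describes raised transaminases and bilirubin in rats and a possible acyl glucuronide metabolite in humans. Participants are healthy volunteers with no expected benefit (Section 3.3.2).

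The individual stopping rule also carries most of the protection against an isolated ALT rise. Appendix 7 makes SAE reporting automatic only when raised bilirubin or INR accompanies it. The dose-escalation stopping rules in Appendix 3 respond to related SAEs, or to related severe AEs in two or more subjects of a cohort.

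**Working it through.** No power, error rate or estimate is involved. The check is whether any text ranks the two instructions, and then how many planned subjects the conflict could reach.

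**Does any text settle it?**

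1. *Appendix 2, note 1.* It cites Section 8.1 and Appendix 7 side by side with no order of precedence.
2. *Section 3.3.1, liver row.* It points to Section 8, where the weaker wording sits.
3. *Section 8.1.3.1.* "Study treatment restart or rechallenge after liver chemistry stopping criteria are met by any participant in this study is not allowed". This bars restart once the criteria are met. It does not say that treatment must be stopped when they are met.
4. *Section 8.1.4.* "If criteria specified for action here are met, actions must be followed". The sentence covers that section's own criteria, and no liver test is among them.
5. *Appendix 7, footnote 1.* "If serum bilirubin fractionation is not immediately available, discontinue study treatment for that subject", but only when ALT ≥3×ULN is accompanied by bilirubin ≥2×ULN. It does not cover an isolated ALT rise, which is the case in dispute.
6. *Appendix 7, column heading.* Labelling the actions as required suggests that Appendix 7 prevails. This is the best evidence available, and it remains an inference.

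No text states which governs.

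**Where can the conflict operate?** It needs drug that can still be stopped. A single bolus is already complete when a post-dose ALT result arrives, so Part A and Cohort 13 are outside its reach. The 7-day infusion cohorts are inside it. Inputs are the cohort sizes in Sections 5.2 and 10.2.1 (8 per cohort: 6 active, 2 placebo).

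- Infusion subjects: Part B 4 × 8 = 32, plus Cohort 14 = 8, total 40.
- On active drug: 4 × 6 + 6 = 30. On placebo: 4 × 2 + 2 = 10.
- Share of planned subjects: 40/112 = 35.7%.
- Bolus only: 64 + 8 = 72. Check: 72 + 40 = 112.

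These are counts of subjects under the ambiguous rule. They are not counts of subjects expected to reach the threshold; the documents give no rate from which to derive that.

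**The case against.** The strongest reply is that the protocol resolves this in practice. Section 8.1.1 is a general paragraph and Appendix 7 is the specific procedure. Section 8.1.1 lists no required actions, so a reference to required actions in Appendix 2 must mean Appendix 7. An investigator who follows Appendix 7 satisfies both texts. This stands as the sensible reading and softens the conflict. It does not remove it, because Section 8.1.1 still tells the investigator that stopping is a matter for consideration, and no sentence subordinates it.

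A second reply is that the algorithm cannot be seen in the text available, and may cover lesser abnormalities for which consideration is the right standard. That is fair. A figure may have been lost in extraction, so its absence is not counted as an error. It is also why the algorithm should not be deleted. The verb in 8.1.1 nonetheless applies to every condition in it, with no exception for the Appendix 7 threshold.

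Third, a reader might infer that liver tests are the only stopping rule left to discretion. The documents do not support that. The QTc rule is mandatory ("a healthy volunteer that meets either bulleted criterion below will be withdrawn from the study"), but Section 8.1.4 leaves discontinuation for psychological distress to the investigators' clinical evaluation. The case rests on the clash with Appendix 7, not on contrast with the neighbouring rules.

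Finally, Section 5.1 plans a review of Part A data before Parts B and C, with changes to dosing, observation period and assessments by amendment as appropriate. The stopping rules are not named there, but the infusion text was open to amendment before anyone received an infusion.

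**Conclusion.** The inconsistency is real and should be corrected. Section 8.1.1 is wrong as written for ALT ≥3×ULN, because it makes discretionary a step that Appendix 7 requires, and precedence has to be inferred. Its reach by design is 40 of 112 planned subjects (36%), 30 of them on active drug, assuming the planned cohort sizes and that a completed bolus leaves nothing to stop.

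Two stronger readings are tempting and should not be drawn:

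- *A quantity of extra drug.* A reader might reason from the daily LFTs and 24-hour sponsor reporting that one additional infusion day is the likely cost. The 24-hour report sits in the same Appendix 7 list as the immediate stop, so that estimate assumes an investigator who obeys one item and ignores the other. Nothing says the sponsor would end the infusion within a day, and the repeat-test window for an isolated ALT rise is 24–72 hours. No extra-exposure figure is supportable.
- *Harm or a compromised result.* The SAP introduction records termination after Cohort 3 sentinel dosing in Part A. No infusion cohort was dosed, so no subject's exposure and no reported result is affected by this wording.

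What remains is a defect in a safety rule as written for healthy volunteers, worth correcting before the text is used for any infusion cohort or carried into a later protocol.

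**What to change.** In Section 8.1.1, state that study treatment must be discontinued immediately when the Appendix 7 liver stopping event (ALT ≥3×ULN) occurs. Add a citation to Appendix 7 alongside any existing algorithm, not in its place, so that no condition shown there is lost. Keep the investigator's discretion, including the best-interest ground, for liver abnormalities below that threshold.

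The cost is about one sentence and a cross-reference. Assessments, schedule and analysis do not change. Any amendment following the planned review before Parts B and C would have been a natural vehicle.
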